12.6.2 Overall Best Response Assessment

Each patient will be classified according to his “best response” for the purposes of analysis of treatment effect. Best response is determined from the sequence of the overall response assessments as described in [Section 12.8](#).

12.7 Response Criteria for Patients with CNS Tumors**12.7.1 Measurable Disease**

Any lesion that is at minimum 10 mm in one dimension on standard MRI or CT, for CNS tumors.

12.7.2 Evaluable Disease

Evaluable disease is defined as at least one lesion, with no lesion that can be accurately measured in at least one dimension. Such lesions may be evaluable by nuclear medicine techniques, immunocytochemistry techniques, tumor markers, CSF cytology, or other reliable measures.

12.7.3 Selection of Target and Non-Target Lesions

For most CNS tumors, only one lesion/mass is present and therefore is considered a “target” for measurement/follow up to assess for tumor progression/response. If multiple measurable lesions are present, up to 5 should be selected as “target” lesions. Target lesions should be selected on the basis of size and suitability for accurate repeated measurements. All other lesions will be followed as non-target lesions. The lower size limit of the target lesion(s) should be at least twice the thickness of the slices showing the tumor to decrease the partial volume effect (e.g., 8 mm lesion for a 4 mm slice).

Any change in size of non-target lesions should be noted, though does not need to be measured.

12.7.4 Response Criteria for Target Lesions

Response criteria are assessed based on the product of the longest diameter and its longest perpendicular diameter. Development of new disease or progression in any established lesions is considered progressive disease, regardless of response in other lesions – e.g., when multiple lesions show opposite responses, the progressive disease takes precedence. Response Criteria for target lesions:

- **Complete Response (CR):** Disappearance of all target lesions.
- **Partial response (PR):** $\geq 50\%$ decrease in the sum of the products of the two perpendicular diameters of all target lesions (up to 5), taking as reference the initial baseline measurements.
- **Stable Disease (SD):** Neither sufficient decrease in the sum of the products of the two perpendicular diameters of all target lesions to qualify for PR, nor sufficient increase in a single target lesion to qualify for PD.

- **Progressive Disease (PD):** 25% or more increase in the sum of the products of the perpendicular diameters of the target lesions, taking as reference the smallest sum of the products observed since the start of treatment, or the appearance of one or more new lesions.

12.7.5 Response Criteria for Non-Target Lesions:

- **Complete Response (CR):** Disappearance of all non-target lesions.
- **Incomplete Response/Stable Disease (IR/SD):** The persistence of one or more non-target lesions.
- **Progressive Disease (PD):** The appearance of one or more new lesions and/or unequivocal progression of existing non-target lesions.

12.7.6 Response criteria for tumor markers (if available):

Tumor markers will be classified simply as being at normal levels or at abnormally high levels.

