4.1 Inclusion Criteria

4.1.1 Age: Patients must be ≥ 2 and ≤ 18 years of age at the time of study enrollment.

4.1.2 Body Surface Area (BSA): Patients must have a body surface area $\geq 0.44 \text{ m}^2$ when enrolling on dose level -1. Patients must have a body surface area $\geq 0.35 \text{ m}^2$ when enrolling on dose levels 1, 2, or 3.

4.1.3 Diagnosis:

Part A: Patients with relapsed or refractory solid tumors (excluding medullary thyroid cancer) including CNS tumors and malignant melanoma are eligible. Patients must have had histologic verification of malignancy at original diagnosis or relapse except in patients with intrinsic brain stem tumors, optic pathway gliomas, or patients with pineal tumors and elevations of CSF or serum tumor markers including alpha-fetoprotein or beta-HCG.

Part B: Patients with medullary thyroid cancer (MTC), with or without bone marrow involvement, will be eligible for Part B. These patients will be enrolled at Dose Level 2, the recommended Phase 2 Dose determined in the dose escalation part of the study.

4.1.4 **Disease Status:**
Patients must have either measurable or evaluable disease (see Sections [12.2](#) and [12.3](#) for definitions).

4.1.5 **Therapeutic Options:** Patient's current disease state must be one for which there is no known curative therapy or therapy proven to prolong survival with an acceptable quality of life.

4.1.6 **Performance Level:** Karnofsky $\geq 50\%$ for patients > 16 years of age and Lansky ≥ 50 for patients ≤ 16 years of age (See [Appendix I](#)). Note: Neurologic deficits in patients with CNS tumors must have been relatively stable for at least 7 days prior to study enrollment. Patients who are unable to walk because of paralysis, but who are up in a wheelchair, will be considered ambulatory for the purpose of assessing the performance score.

4.1.7 **Prior Therapy**

4.1.7.1 Patients must have fully recovered from the acute toxic effects of all prior anti-cancer chemotherapy.

- a. **Myelosuppressive chemotherapy:**
At least 21 days after the last dose of myelosuppressive chemotherapy (42 days if prior nitrosourea).

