8.3 Radiology Studies

8.3.1 Bone Age/ Knee MRI

All tibial radiographs and knee MRIs (if obtained) should be submitted for Central Review.

8.3.2 Central Radiology Review for Response:

Patients who respond (CR, PR) to therapy or have long term stable disease (SD) (≥ 6 cycles) on protocol therapy will be centrally reviewed. COG Operations Center will notify the Imaging Center of any patient requiring central review. The Imaging Center will then request that the treating institution forward the requested images for central review. The central image evaluation results will be entered into RAVE for review by the COG Operations Center and for data analysis.

The images are to be forwarded electronically to the Imaging Research Center at Children's Hospital Los Angeles via the grid.

COG institutions that are not connected to the grid can send the images on hard copy film, CD ROM, or by FTP. Submitted imaging studies should be clearly marked with the COG patient ID, study number (ADVL1211) and date and shipped to [name] at the address below:

[name]
Imaging Research Center
Data Administrator
Children's Hospital Los Angeles
[name]
Los Angeles, CA 90027
[contact]
[contact]
E-mail: [contact]

8.4 **Pharmacology COMPLETE**

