12.7.7 Overall Response Assessment

The overall response assessment takes into account response in both target and non-target lesions, the appearance of new lesions and normalization of markers (where applicable), according to the criteria described in the table below. The overall response assessment is shown in the last column, and depends on the assessments of target, non-target, marker and new lesions in the preceding columns.

Target Lesions	Non-target Lesions	Markers	New Lesions	Overall Response
CR	CR	Normal	No	CR
CR	IR/SD	Normal	No	PR
CR	CR, IR/SD	Abnormal	No	PR
PR	CR, IR/SD	Any	No	PR
SD	CR, IR/SD	Any	No	SD
PD	Any	Any	Yes or No	PD
Any	PD	Any	Yes or No	PD
Any	Any	Any	Yes	PD

Each patient will be classified according to his “best response” for the purposes of analysis of treatment effect. Best response is determined as outlined in Section 12.8 from a sequence of overall response assessments.

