12.8 Best Response

12.8.1 Evaluation of Best Overall Response

The best overall response is the best response recorded from the start of the treatment until disease progression/recurrence (taking as reference for progressive disease the smallest measurements recorded since the treatment started). The patient's best response assignment will depend on the achievement of both measurement and confirmation criteria.

Table 1: For Patients with Measurable Disease (i.e., Target Disease)

Target Lesions	Non-Target Lesions	New Lesions	Overall Response	Best Overall Response when Confirmation is Required*
CR	CR	No	CR	≥28 days Confirmation**
CR	Non-CR/Non-PD	No	PR	≥28 days Confirmation**
CR	Not evaluated	No	PR	
PR	Non-CR/Non-PD/not evaluated	No	PR	
SD	Non-CR/Non-PD/not evaluated	No	SD	documented at least once ≥28 days from baseline**
PD	Any	Yes or No	PD	no prior SD, PR or CR
Any	PD***	Yes or No	PD	
Any	Any	Yes	PD	

* See RECIST 1.1 manuscript for further details on what is evidence of a new lesion.
** Only for non-randomized trials with response as primary endpoint.
*** In exceptional circumstances, unequivocal progression in non-target lesions may be accepted as disease progression.

Note: Patients with a global deterioration of health status requiring discontinuation of treatment without objective evidence of disease progression at that time should be reported as “*symptomatic deterioration*.” Every effort should be made to document the objective progression even after discontinuation of treatment.

Table 2: For Patients with Non-Measurable Disease (i.e., Non-Target Disease)

Non-Target Lesions	New Lesions	Overall Response
CR	No	CR
Non-CR/non-PD	No	Non-CR/non-PD*
Not all evaluated	No	not evaluated
Unequivocal PD	Yes or No	PD
Any	Yes	PD

* ‘Non-CR/non-PD’ is preferred over ‘stable disease’ for non-target disease since SD is increasingly used as an endpoint for assessment of efficacy in some trials so to assign this category when no lesions can be measured is not advised

Table 3. Sequences of overall response assessments with corresponding best response.

1 st Assessment	2 nd Assessment	Best Response
Progression		Progressive disease
Stable, PR, CR	Progression	Progressive disease
Stable	Stable	Stable
Stable	PR, CR	Stable
Stable	Not done	Not RECIST classifiable
PR	PR	PR
PR	CR	PR
PR, CR	Not done	Not RECIST classifiable
CR	CR	CR

Table 4: Overall Response for Patients with Neuroblastoma and Measurable Disease

CT/MRI	MIBG	Bone Scan	Bone Marrow	Catechol	Overall

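### Section 12.7.4 judges CNS target-lesion progression per lesion in two places, with no percentage, and on the sum in the PD bullet, so a multi-lesion scan can be both PR and PD, or fit no bullet.

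*Combined protocol and SAP*

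**What the plan says.** All of the following is in section 12.7.4 of the combined protocol and SAP unless stated.

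- **Lead-in:** "progression in any established lesions is considered progressive disease, regardless of response in other lesions". It adds that progression takes precedence when lesions respond in opposite directions. No percentage is given.
- **PR bullet:** a fall of at least 50% in the sum of products of perpendicular diameters, from baseline. It has no exclusion for a lesion that is growing.
- **SD bullet:** the first half is on the sum (not enough shrinkage for PR). The second half is per lesion: "nor sufficient increase in a single target lesion to qualify for PD".
- **PD bullet:** "25% or more increase in the sum of the products of the perpendicular diameters of the target lesions", measured from the smallest sum since treatment began, or a new lesion. This is the only progression rule with a number.

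Elsewhere, section 12.7.3 allows up to five target lesions but notes: "For most CNS tumors, only one lesion/mass is present". Section 12.7.5 covers non-target lesions. The overall response in section 12.7.7 "depends on the assessments of target, non-target, marker and new lesions in the preceding columns", so it takes the target category as given. Section 12.8.1 supplies only a general reference, "taking as reference for progressive disease the smallest measurements recorded since the treatment started", and does not say whether it applies to each lesion or to the sum. CNS patients enter through Part A, which section 4.1.3 opens to patients with "relapsed or refractory solid tumors (excluding medullary thyroid cancer) including CNS tumors".

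**The concern.** A progression rule should put each scan in one category. Here the unit changes between the lead-in, the two halves of the SD bullet, and the PD and PR bullets. With one target lesion the sum is the lesion and nothing is lost. With two or more, the outcome depends on which sentence the assessor applies.

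The category has consequences. Radiographic progression is a criterion for removal from protocol therapy (section 10.1a), and a new cycle requires at least stable disease (section 5.2). It also feeds the reported result: in Table 3 of section 12.8.1, a PR, CR or stable assessment followed by progression gives a best response of progressive disease.

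**Working it through.** The plan has no sample-size, power or alpha figure to reproduce here. The check classifies example scans under each sentence. Lesion products (mm²) are illustrative. The documents give no single-lesion percentage, so 25% is assumed, borrowed from the PD bullet. In both examples the baseline is also the smallest value before the scan.

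**Example 1: PR against PD.** Two lesions, 900 and 100, become 300 and 180.
- Sum: (300 + 180) / (900 + 100) = 480 / 1000 = 0.48, a fall of 52%. The PR bullet is met.
- Second lesion: 180 / 100 = 1.80, a rise of 80%. The lead-in makes this PD despite the response in the other lesion. This holds for any single-lesion threshold up to 80%.

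**Example 2: PD against no category.** Two lesions, 400 and 400, become 400 and 520.
- Sum: 920 / 800 = 1.15, a rise of 15%. The PD bullet is not met.
- Second lesion: 520 / 400 = 1.30, a rise of 30%. The lead-in makes this PD.
- The SD bullet rules out SD when a single lesion has grown enough, so at a 25% threshold the scan is not SD either. The bullets leave it unclassified.

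**Width of the gap.** Take k equal lesions, one growing by g% and the rest unchanged. The sum rises by g/k %, so sum-based PD needs g = 25k. The readings disagree when g is at least 25% but below:

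| k | Upper limit of g |
|---|---|
| 2 | 50% |
| 3 | 75% |
| 4 | 100% |
| 5 | 125% |

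**Direction.** At 25% the disagreement runs one way. If every lesion is below 1.25 times its value at the scan with the smallest sum, the total is below 1.25 times that sum. So sum-based PD always implies that some lesion is up at least 25%. At a higher single-lesion threshold this fails. With 40%, 400 + 400 becoming 520 + 520 is 1040 / 800 = 1.30, which is PD on the sum, while neither lesion reaches 40%.

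**Cost of a per-lesion rule.** Assume independent measurement error with SD 0.5 to 1.0 mm per diameter (not in the documents), two truly stable 10 × 10 mm lesions, one baseline scan and one follow-up scan. In 1,000,000 simulated draws per SD, false PD occurs as follows:

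| Rule | SD 0.5 mm | SD 1.0 mm |
|---|---|---|
| Any lesion up 25% | about 2.6% | about 25% |
| Sum up 25% | about 0.1% | about 6% |

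Small lesions are the reason. 10 × √1.25 = 11.18 mm, so about 1.2 mm in each diameter is enough. A lesion that has shrunk to 5 × 5 mm needs only 5 × √1.25 = 5.59 mm, about 0.6 mm in each.

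**The case against.** The strongest defence is that the lead-in already settles mixed responses. It can be read in two ways.

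- **Lesion by lesion.** PD then overrides PR, and Example 1 is PD. The precedence question is answered, but the rule cannot be applied because the percentage and the reference value for one lesion are missing. The PR bullet still needs the exclusion.
- **Precedence among target disease, non-target disease and new lesions.** This is what the last three rows of the section 12.7.7 table implement. The PD bullet then supplies the only threshold, and the defect shrinks to one phrase in the SD bullet. The lead-in's own example, several lesions responding in opposite directions, fits this reading less well.

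Either reading leaves text to correct, and the documents do not choose between them.

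A reader might infer that Example 2 is SD by the bullets. The text does not support that. The SD bullet excludes a sufficiently grown single lesion, and calling the scan SD means treating that phrase as shorthand for the sum, which is not stated. A reader might also infer that the protocol intends a 25% per-lesion rule. No per-lesion percentage appears anywhere.

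The safeguards partly stand. Section 8.3.2 sends for central review "Patients who respond (CR, PR) to therapy or have long term stable disease (SD" lasting at least six cycles), so a site that calls PR on the sum is checked. A site call of PD is not itself a trigger. Section 10.1 also permits removal for clinical progression or on the physician's judgement. Finally, the documents do not show whether any CNS patient is still on therapy. The section 8.1 footnotes about currently enrolled patients name only Part B, the medullary thyroid cancer stratum.

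**Conclusion.** The inconsistency is in the current text, and sections 12.7.5, 12.7.7 and 12.8 do not resolve it. For a CNS patient with two or more target lesions, one scan can be PR by its bullet and PD by the lead-in, or PD by the lead-in and in no bullet category. The second case rests on the assumed 25% single-lesion threshold and holds for any threshold up to 30%.

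Severity is the lowest. The affected group is the multi-lesion part of the CNS patients in Part A. Its size is not given, and the whole study is capped at 41 patients of all tumor types (section 11.1). Response is a secondary aim (section 1.2) analyzed descriptively (section 11.5). A reader might infer that the dose or toxicity conclusions are at risk, but the dose-limiting toxicity definitions in section 5.5 do not use tumor response. A benefit to patients still on therapy is not shown, so the clearest gain is consistent reporting.

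**What to change.** Use one unit throughout section 12.7.4.

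**Default, with no new threshold:** keep the stated sum rule. In the SD bullet, replace the reference to a single target lesion with the sum of products. Limit the lead-in's precedence to sum-based target PD, new lesions and unequivocal non-target progression, as the section 12.7.7 table already does. Example 1 is then PR and Example 2 is SD. The cost is two wording changes. The price clinically is that growth confined to one of several target lesions counts as PD only when it raises the sum by 25%.

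**If the sponsor intended per-lesion progression:** the PD bullet must state the percentage, each lesion's reference value, a minimum absolute increase, and how to handle a lesion that has disappeared (a percentage rise from zero is undefined). PR and SD must require that no target lesion meets the rule. Both examples are then PD at 25%, provided the absolute minimum is also met. The downside is more false PD from measurement noise in small lesions, with removal from therapy as the result.

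**Either way:** list each multi-lesion CNS patient whose response or progression date differs between the two readings, and state the single-lesion threshold used for the listing. This uses measurements already taken.

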12.7.7 Overall Response Assessment

The overall response assessment takes into account response in both target and non-target lesions, the appearance of new lesions and normalization of markers (where applicable), according to the criteria described in the table below. The overall response assessment is shown in the last column, and depends on the assessments of target, non-target, marker and new lesions in the preceding columns.

Target Lesions	Non-target Lesions	Markers	New Lesions	Overall Response
CR	CR	Normal	No	CR
CR	IR/SD	Normal	No	PR
CR	CR, IR/SD	Abnormal	No	PR
PR	CR, IR/SD	Any	No	PR
SD	CR, IR/SD	Any	No	SD
PD	Any	Any	Yes or No	PD
Any	PD	Any	Yes or No	PD
Any	Any	Any	Yes	PD

Each patient will be classified according to his “best response” for the purposes of analysis of treatment effect. Best response is determined as outlined in Section 12.8 from a sequence of overall response assessments.

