4.2.2 Concomitant Medications

4.2.2.1 Corticosteroids: Patients receiving corticosteroids who have not been on a stable or decreasing dose of corticosteroid for at least 7 days prior to enrollment are not eligible.

4.2.2.2 Investigational Drugs: Patients who are currently receiving another investigational drug are not eligible.

4.2.2.3 Anti-cancer Agents: Patients who are currently receiving other anti-cancer agents are not eligible

4.2.2.4 Anti-GVHD agents post-transplant:

Patients who are receiving cyclosporine, tacrolimus or other agents to prevent graft-versus-host disease post bone marrow transplant are not eligible for this trial.

4.2.2.5 CYP3A4 active agents: Patients must not be receiving any of the following potent CYP3A4 inducers or inhibitors: erythromycin, clarithromycin, ketoconazole, azithromycin, itraconazole, grapefruit juice or St. John's wort. A list of other known CYP3A4 inducers and inhibitors that should be discontinued prior to initiation of protocol therapy and should be avoided during study therapy if reasonable alternatives exist is included in [Appendix IX](#).

4.2.2.6 Patients who are receiving systemic treatment anticoagulation are not eligible. Patients receiving prophylactic systemic anticoagulation will be allowed as long as eligibility PT/INR requirements are met (See [Section 4.1.8.4](#)).

4.2.2.7 Enzyme-inducing Anticonvulsants: Patients must not have received enzyme-inducing anticonvulsants within 14 days prior to enrollment (See [Appendix XIII](#) for a list of unacceptable enzyme inducing anticonvulsants).

4.2.2.8 QTc Agents: Patients who are receiving drugs that prolong QTc are not eligible (See [Appendix XV](#) for a list of agents).

4.2.3 Patients must be able to swallow intact tablets. Patients who cannot swallow intact tablets are not eligible.

4.2.4 Patients with active bleeding are not eligible. Specifically, no clinically significant GI bleeding, GI perforation, intra-abdominal abscess or fistula for 6 months prior to enrollment, no hemoptysis or other signs of pulmonary hemorrhage for 3 months prior to enrollment.

4.2.5 Patients with evidence of an acute intracranial or intratumoral hemorrhage on CT or MRI are not eligible (patients with evidence of resolving hemorrhage will be eligible).

4.2.6 Surgery: Patients who have had or are planning to have the following invasive procedures are not eligible:

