7.5 Concomitant Medications

Proton pump inhibitors (PPIs) and H₂-antagonists should be avoided if possible (See [Section 9.1.6](#)).

Medications that are strong inhibitors or inducers of CYP3A4 should be avoided (see

[Appendix IX](#)). Corticosteroids may induce CYP3A4 and are therefore not routinely recommended on study unless deemed absolutely necessary or when used in stable or decreasing doses from the time of study enrollment.

The use of enzyme inducing anticonvulsants is not permitted. See [Appendix XIII](#) for a list of unacceptable enzyme inducing and recommended non-enzyme inducing anticonvulsants.

XL184 has been associated with prolonged QTc, so medications that prolong QTc are prohibited and medications that may prolong QTc should be avoided when possible (see [Appendix XV](#)).

7.6 **Surgery**

Patients should not have elective surgical procedures while on therapy. For patients who require emergent or urgent procedures, therapy may not be restarted until 28 days after major procedures and 7 days after minor procedures such as line replacement (3 days for external lines [e.g. Hickman or Broviac]), as detailed in [section 4.2.6](#).

7.7 **Concurrent Anti-Hypertensive Therapy**

The algorithm in [Section 6.4](#) will be used to grade and manage XL184 related hypertension. Should initiation of anti-hypertensive therapy be required, single agent therapy (commonly including the calcium channel blockers amlodipine or nifedipine, which are permissible without discussion with the study chair) should be started and the blood pressure should be monitored at least twice weekly until BP is within the 95th percentile for age, height, and gender per [Section 6.4](#).

7.8 **Management of Hypothyroidism**

Patients with Grade 2 hypothyroidism adequately managed with thyroid hormone replacement may continue on protocol therapy. Patients with Grade 3 or greater hypothyroidism will be considered to have had a dose-limiting toxicity. These patients should be managed according to [Section 6.2](#) and should also be evaluated by an endocrinologist for further management. Patients who enter the study on thyroid replacement should have their medication adjusted to maintain TSH in the normal range.

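### CNS response is scored without regard to corticosteroid dose, so a response or stable disease on a raised steroid dose could be read as treatment effect

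*Combined protocol and SAP*

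**What the plan says.** **Scoring.** For CNS tumors, PR in Section 12.7.4 is a fall of at least 50% in the "sum of the products of the two perpendicular diameters of all target lesions (up to 5), taking as reference the initial baseline measurements". PD is a "25% or more increase in the sum of the products of the perpendicular diameters of the target lesions" relative to the smallest sum since treatment began, or a new lesion. SD is what lies between. Section 12.7.7 then combines the inputs: "The overall response assessment takes into account response in both target and non-target lesions, the appearance of new lesions and normalization of markers". The overall response "depends on the assessments of target, non-target, marker and new lesions in the preceding columns". It then sends the sequence of assessments to Section 12.8 for best response, which is used to analyse treatment effect.

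**Steroids at entry.** Under Section 4.2.2.1, patients on corticosteroids who "have not been on a stable or decreasing dose of corticosteroid for at least 7 days prior to enrollment are not eligible".

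**Steroids on study.** Section 7.5 says corticosteroids may induce CYP3A4 and are "not routinely recommended on study unless deemed absolutely necessary or when used in stable or decreasing doses from the time of study enrollment". The two conditions are joined by an or, so the first covers a new or increased dose.

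**Use of the result.** Antitumor activity is secondary aim 1.2.1. Section 11.5 reports response descriptively and calls these analyses exploratory.

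**The concern.** That steroids can reduce edema and apparent lesion size in CNS tumors is general clinical knowledge, not something the documents state. If it happens here, the written rules cannot tell it apart from a drug effect. The protocol treats a rising steroid dose as a concern at entry and discourages it on study, yet the response table has no place to take it into account. The trial has no comparator arm in which the same background change would show up. A reader of the CNS responses would therefore have no means of judging which were recorded on a steroid dose above baseline.

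**Working it through.** The plan states no figure on this point, so the check is mainly a reading of the rules side by side.

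**1. Is a raised dose possible on study?** Yes, as a restricted exception under Section 7.5.

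**2. Does any scoring rule refer to steroid dose?** No. Neither the criteria in 12.7.4 to 12.7.6, the table in 12.7.7, the best-response tables in 12.8, central review in 8.3.2 nor the analysis text in 11.5 mentions it.

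**3. Is the dose captured at the scan?** Not by the schedule. The Section 8.1 table has no row for steroids or concomitant drugs. The patient diary (Appendix III) asks only for a note of other drugs taken.

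**4. What does the table return?** Take a patient on a raised dose with no new lesion and no non-target progression. A fall of at least 50% in the product is PR. Growth held under 25% is SD. No other outcome is available to the assessor.

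**5. How large a change is that?** For one lesion changing equally in both diameters:
- PR threshold: 1 − √0.50 = 0.293, about a 29% fall in each diameter. For example, 30 × 30 mm (900 mm²) to 21 × 21 mm (441 mm²) gives 441/900 = 0.49, a 51% fall.
- PD threshold: √1.25 − 1 = 0.118, about an 11.8% rise in each diameter.

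These figures only restate the thresholds. The documents do not say how much steroids change lesion size.

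**6. Do the safeguards catch it?**

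| Safeguard | What it does | Checks steroid dose? |
|---|---|---|
| Section 12.8, Table 3 | Best response of PR needs PR followed by PR or CR; a response with no second assessment is not classifiable; progression at the second assessment gives PD | No |
| Section 8.1, footnote 8 | Repeat evaluation on the next consecutive cycle after PR or CR | No |
| Section 8.3.2 | Central review of CR, PR, and SD lasting at least 6 cycles; only images are requested | No |
| Section 10.1(a) | Clinical progression can end protocol therapy | No; 12.7 does not use it for scoring |

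Transient shrinkage is largely filtered for PR. A raised dose held across both assessments passes. The filter is weaker for SD: if the first scan is SD and a later steroid increase keeps the second scan under the 25% limit, Table 3 returns stable rather than progressive disease.

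**The case against.** The best case for the plan is that steroid use is already restricted, best response needs two assessments, responders' images are centrally reviewed, clinical progression can end therapy, and the endpoint is descriptive. All of that is true, and it narrows the concern to sustained steroid-related change. It does not remove it, because no step looks at the dose.

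Several stronger readings are tempting but not supported:

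- **That the protocol freely allows steroids, or controls them at entry and then abandons the control.** Section 7.5 carries a restriction on study. A start or increase is the exception.
- **That the bias can run only one way.** Sections 2.3.3 and 9.1.6 list dexamethasone as a strong CYP3A4 inducer, and Section 2.3.3 says such inducers may significantly decrease cabozantinib concentrations. A steroid start could therefore weaken true drug effect. Permitted tapering could push toward apparent progression. The net direction is undetermined.
- **That an SD call keeps a worsening child on therapy.** Section 5.2 permits a further cycle but does not require one. Section 10.1 allows removal for clinical progression or on physician judgment.
- **That the error is worth a stated number of percentage points.** Assuming 5 to 15 evaluable CNS patients, one false PR would be 1/15 = 6.7 to 1/5 = 20 points. The documents give no CNS count and no rate of steroid increases, so this does not estimate the bias.

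**Conclusion.** The concern holds in limited form. Sections 12.7.4 and 12.7.7 can classify a CNS patient as a confirmed PR or SD when the change in lesion size is related to a steroid dose above baseline, and the existing safeguards reduce this without testing for it.

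The conclusion rests on two assumptions from outside the documents: that steroids can alter measured lesion size, and that at least one CNS patient has a raised dose maintained across the relevant scans. How often this occurs, and how far it would move the reported CNS results, cannot be calculated.

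The consequence is confined to the interpretation of secondary aim 1.2.1 in CNS patients. No sample size, DLT rule or dose decision depends on it. The change is worth making because it is cheap and the trial has no control arm.

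**What to change.** - **Record** the corticosteroid dose at baseline and at each CNS disease evaluation, including the confirmatory scan. For patients already treated, it would have to come from the medical record and diary notes.
- **Add to Section 12.7.7, for the response analysis only,** that CR or PR is not credited at a time point when the steroid dose is above baseline. Keep these patients in the response-rate denominator as non-responders. Scoring them not evaluable could remove worsening patients and inflate the rate.
- **Report SD at a raised dose separately,** with steroid status, rather than dropping it.
- **List steroid status** (raised, stable or reduced) beside every CNS response, so that tapering is visible too.
- **State that a raised dose alone is not PD.**
- **State that this scoring does not change treatment continuation.** The sponsor should say how it relates to the stable-disease condition in Section 5.2.

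The cost is one data field per CNS evaluation and a few lines of text. A genuine response on steroids raised for a non-tumor reason may go uncredited, so the CNS response rate may be slightly lower.
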